#### **DISCONTINUATION OF STUDY:**

The study will be discontinued:

- If any subject has an adverse event leading to respiratory failure requiring resuscitation or death from the investigational product,
- If two or more incidences in the pAF group of wounds require emergent surgical intervention or disseminated infections requiring hospitalization,
- At the discretion of the Data Safety Monitoring Board (DSMB). The DSMB will meet regularly to review adverse events, safety analyses, and study data. The DSMB will have access to the actual treatment assignments for each group.

## **8- STATISTICAL CONSIDERATIONS**

### **Statistical Method**

This is a modest feasibility study with subjects randomized to two groups: (1) treatment group with pAF applied to the randomized wound ( $n=30 \pm 2$  patients expected), (2) control group, with wounds receiving standard of care treatment ( $n=30 \pm 2$  patients expected).

Feasibility will be demonstrated if the study's clinical wound care providers are able to successfully apply pAF to the wounds in this clinical study situation. Any issues or concerns that occur will be recorded and reported descriptively in a similar fashion to safety outcomes (described below). As no issues or concerns are expected, it should be clear from this descriptive analysis if feasibility of applying pAF is demonstrated.

*Primary Endpoint:* Whether the patient experienced any post-randomization, study-related SAEs while on study.

For the definition of the primary endpoint, a serious adverse event (SAE) is considered study-related if the medical monitor concludes the SAE is either possibly related or probably related to study participation.

Safety will be assessed by descriptive reporting of the incidence proportion of study-related serious adverse events in each study group, with one-sided 95% binomial exact confidence intervals. No statistical hypothesis test is planned to assess safety, which is consistent even with large Phase III trials. The table below displays the number of subjects, out of 30, experiencing no related SAE and the corresponding lower-bound of the 95% exact confidence interval.

Number of Subjects with no Study-related Serious Adverse Events	Number of Subjects Experiencing any Study-related Serious Adverse Events	Lower-bound of the 95% Exact Binomial Confidence Interval for Safety
30	0	90%
29	1	85%
28	2	80%
27	3	76%

If there are 30 subjects in the pAF group and if all subjects in the pAF group complete the study without experiencing any study-related SAEs, we will be able to state with 95% confidence that the safety of pAF is at least 90%.

Exploratory outcomes for safety include, but are not limited to, the following:

- Whether the patient experienced any post-randomization SAEs while on study (regardless of relatedness to study participation)
- Whether the patient experienced any post-randomization related AEs while on study
- Whether the patient experienced any post-randomization unexpected AEs while on study.

*Secondary Endpoint: The percent reduction in wound area at Visit 5 relative to the size at randomization (Visit 2), per the imaging software assessments.*

The inclusion criteria limit the study to wounds which are difficult to heal, explaining why patients are not randomized if the wound area shrinks significantly between Visits 1 and 2. Therefore, greater reduction in wound size with pAF, than with SOC will suggest efficacy of pAF for wound treatment. To describe a trend in a statistical hypothesis testing framework, the following two-sided hypothesis will be assessed:

$$H_0: \mu_{\text{pAF}} = \mu_{\text{SOC}} \text{ versus } H_1: \mu_{\text{pAF}} \neq \mu_{\text{SOC}}$$

The secondary outcome variable will be the reduction in wound size at Visit 5 relative to the Visit 2 wound size (i.e.,  $100\% * (1 - \text{Visit 5 wound area} / \text{Visit 2 wound area})$ ), with all measurements expressed as the approximate area determined by the imaging software. Wound size should be measured at all study visits. To provide an intuitive effect size, percentage change from Visit 2 will be computed at visits 3, 4, and 5 (approximately 6, 12, and 25 weeks after randomization) with the changes at visits 3 and 4 considered as exploratory outcomes. If there are study visits outside of the visit's +/- 1 week window, all percentages will be divided by the number of elapsed days since Visit 2, so the outcome is expressed as a percentage change per day. If the change in wound size at Visit 5 follows a symmetric distribution a two-sample t-test will be performed, otherwise a Wilcoxon rank sum test will be used. As exploratory analyses, the prescribed analytic approach will be applied to the exploratory endpoints of percent reduction in wound area at Visit 3 and percent reduction in wound area at Visit 4.

If enrolled subjects have multiple wounds that meet size requirements (according to the eligibility criteria) the largest wound will be identified as the primary wound, while all others will be identified as target wounds. Data may be collected on the target wounds and used only for exploratory purposes. The largest wound that is randomized to the treatment or standard of care, will be selected as the primary wound for the hypothesis test just described because it is the only wound with randomized treatment; other wounds on the subject are to receive standard-of-care treatment. Data will be collected on the primary wound for analyses. Wounds that are contiguous are treated as one wound. Over the course of the study, if the index wound (i.e., the wound randomized to treatment) becomes contiguous with one or more extant wounds, the “merged” wounds will be regarded as the wound going forward but not retrospectively. It is not anticipated that disconnected wounds will become contiguous over the course of the study.

An exploratory endpoint is whether or not a wound is closed at Visit 5 (the last specified follow-up visit). Fisher’s exact test will be used to test for an association between treatment arm and whether the wound is closed at Visit 5.

Descriptive summaries will also be provided by treatment arm for the following additional exploratory endpoints: the proportion of wounds that have recurred at Visit 5; the percent reduction (relative to Visit 2) in the maximal depth of the wound at Visits 3, 4, and 5; the change since Visit 2 in wound-associated pain at Visits 3, 4, and 5; the presence of hypertrophic scar formation at Visit 5 (measured with modified Vancouver Scar Scale); and incidence of wound infection as determined by wound culture/assessment from Visit 4.

The primary analysis of the primary outcome implicitly adopts a last-observation-carried-forward approach. Multiple imputation will be used for the primary analysis of the secondary outcome and may also be used for other outcomes, as described in the Statistical Analysis Plan. Because the sample size is modest, it may not be feasible to use complex multiple imputation models, but candidate variables for the imputation of missing values for the secondary outcome will include variables such as assigned treatment arm and wound area measurements from other study visits. As sensitivity analyses, the analyses of the primary and secondary outcomes will be repeated twice, first replacing each missing outcome with the lowest observed outcome at that timepoint from among subjects in the same assigned treatment arm, and then again replacing each missing outcome with the highest observed outcome at that timepoint from among subjects in the same assigned arm.

A number of additional prespecified exploratory analyses will be conducted. Although the overall sample size is modest, subgroup analyses were requested by the FDA and will be conducted for the primary and secondary outcomes using subgroups defined by the following variables: sex; race; ethnicity; diagnosis of diabetes mellitus or a screening hemoglobin A1C greater than or equal to 6.5; use of immunosuppressive medications; presence/absence of known malignancy other than non-metastatic basal or squamous cell carcinoma; nutritional status as defined by albumin levels; presence/absence of blood coagulation conditions defined by PT/INR and PTT levels; presence/absence of venous vascular disease affecting the wound area; presence/absence of arterial vascular disease affecting the wound area; Visit

1 oxygen saturation  $<90\%$  or  $\geq 90\%$ ; and concomitant anticoagulation medication or lack thereof. The details of the subgroup analysis will be available in the Statistical Analysis Plan (SAP).

Finally, although some additional collected data elements may influence the response, the primary and secondary analyses will not adjust for these other characteristics because the modest sample size makes such adjustments impractical. The randomization procedure will be relied upon to avoid favoring either treatment arm in the safety and efficacy comparisons. Exploratory analyses may be conducted to attempt to adjust for one or more additional variables.

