The goal of our study is to assess, in an outpatient setting, the safety and healing in chronic wounds treated with pAF. We will include patients with upper or lower extremity full thickness wounds (including thermal) that are greater than 3 months old and less than 12 months old and who are able to complete required site study visits and procedures in good faith. The wound size must be greater than or equal to 5cm^2 and less than 75 cm^2. We will exclude anyone that is admitted to the hospital at the time of enrollment, is less than 18 years old or older than 85 years old, is known to be pregnant or planning to become pregnant (including women of childbearing potential who are unwilling to use effective birth control while participating in the study), is breastfeeding, has suspicion of osteomyelitis, has received or plans to receive an investigational agent or intervention, requires skin grafting, has wounds with sinus tracts, has a diagnosed highly disruptive uncontrolled mental health disorder, or has a known history of prior drug abuse. Our primary objective is to determine

the safety of using pAF to treat patients with chronic wounds and our secondary objective is to assess the reduction in wound size after application of pAF compared to standard of care.

Cases #1 & 2 show preliminary results that we have obtained with pAF applications when applied to refractory chronic wounds (>12 months without healing).

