Only the wound randomized to treatment is considered for the secondary outcome. Other wounds are to receive standard-of-care and measurements on other wounds are only applicable, if at all, to exploratory analyses. See the protocol for further details.

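### If the randomised wound merges with another, the later area covers both wounds but the Visit 2 area covers one, so the percent reduction compares different tissue

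*Protocol*

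**What the plan says.** Protocol section 8 (Statistical Method, Secondary Endpoint) defines the outcome: "The secondary outcome variable will be the reduction in wound size at Visit 5 relative to the Visit 2 wound size", that is, 100% × (1 − Visit 5 area / Visit 2 area), with areas from the imaging software. SAP 7.3 gives the same formula for Visits 3, 4 and 5. Neither formula has a term for merging.

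The merge rule is in the same protocol section. It applies "if the index wound (i.e., the wound randomized to treatment) becomes contiguous with one or more extant wounds", and the merged wounds then "will be regarded as the wound going forward but not retrospectively". The protocol adds: "It is not anticipated that disconnected wounds will become contiguous over the course of the study". On other qualifying wounds it says: "Data may be collected on the target wounds and used only for exploratory purposes".

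The SAP has no merge rule. Section 7.3 says "Only the wound randomized to treatment is considered for the secondary outcome" and that "measurements on other wounds are only applicable, if at all, to exploratory analyses", and then sends the reader to the protocol for details.

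**The concern.** Read together, the formula and the merge rule change what is measured between the two visits. At Visit 2 the area is that of the index wound. After a merge, the later area is that of the index wound plus its neighbour. The score falls by the neighbour's whole area even if nothing has grown.

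The neighbour was not randomised and receives standard of care, so in the pAF arm its area enters the one efficacy outcome that is tested outside the exploratory set. The outcome cannot exceed +100% but has no fixed floor. With about 30 subjects per arm, a single such value can move an arm's mean and standard deviation.

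There are two knock-on effects. Merged areas would enter the pool of wound areas used for imputation (SAP 5.2). A merged score could also become the lowest observed value, which the sensitivity analysis in SAP 7.3.1 assigns to every missing outcome in that arm.

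**Working it through.** **Inputs from the documents.** Outcome formula and merge rule: Protocol section 8 and SAP 7.3. Power scenario, SAP section 8: 30 per arm, all observed; closure probability 0.2 (SOC) and 0.5 (pAF); unclosed wounds uniform between 0% and 100%; Wilcoxon power about 54%. Two-sided 0.05 level: SAP 7.3.

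**Assumptions.** The documents give no merge rate and no neighbour areas. The wound areas, the number of merges and the neighbour's relative size below are assumed. Merges are placed on unclosed wounds.

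**1. The SAP's own figure.** A simulation of 30,000 trials gives Wilcoxon power of 54.6% (54.3% with continuity correction), which reproduces the 54%. The unpooled t-test gives 42.3%. The mean difference is 15.1 points; by hand it is (0.5×100 + 0.5×50) − (0.2×100 + 0.8×50) = 75 − 60 = 15.

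**2. The rule in symbols.** Let I2 and I5 be the index area at Visits 2 and 5, and N2 and N5 the neighbour's.

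- Rule as written: 100 × (1 − (I5 + N5)/I2). This equals the index-only score minus 100 × N5/I2.
- Like-for-like: 100 × (1 − (I5 + N5)/(I2 + N2)).

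The score as written is negative whenever N5 exceeds I2 − I5, the area the index wound has lost.

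| Index V2→V5 (cm²) | Neighbour V2→V5 (cm²) | Index alone | As written | Like-for-like |
|---|---|---|---|---|
| 20→20 | 15→15 | 0% | −75% | 0% |
| 20→16 | 18→16 | +20% | −60% | +15.8% |
| 20→14 | 15→18 | +30% | −60% | +8.6% |
| 20→14 | 5→6 | +30% | 0% | +20% |

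The index wound is the largest qualifying wound, so one qualifying neighbour has N2 ≤ I2. If neither wound has grown, (I5 + N5)/I2 ≤ 2 and the score cannot fall below −100%.

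**3. Effect on the comparison.** Assume the neighbour is 0.9 times the index area and unchanged. By hand, for one pAF merge:

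- As written, that wound loses 90 points and the arm mean loses 90/30 = 3.0, so the difference is 15 − 3.0 = 12.0.
- Like-for-like, the score is the index reduction divided by 1.9. Its expected value falls from 50 to 26.3, the arm mean loses 23.7/30 = 0.8, and the difference is 14.2.

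Simulation, 8,000 trials per merge row (Monte Carlo standard error at most √(0.25/8000) = 0.6 points):

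| Merges | Scoring | Mean difference | Wilcoxon power | Unpooled t power |
|---|---|---|---|---|
| None | – | 15.1 | 54.6% | 42.3% |
| One pAF | as written | 12.0 | 47.0% | 23.6% |
| One pAF | like-for-like | 14.2 | 50.6% | 37.9% |
| One SOC | as written | 17.9 | 58.9% | 50.0% |
| One SOC | like-for-like | 15.8 | 56.7% | 45.4% |
| One in each | as written | 15.1 | 51.9% | 30.0% |
| One in each | like-for-like | 14.9 | 52.0% | 40.2% |

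**4. The static pair.** Set one unclosed pAF wound to −75% (as written) or to 0% (like-for-like). Wilcoxon power is 46.6% in both cases. The planning model has no values below zero, so either score takes the lowest rank. Unpooled t-test power is 16% against 32%.

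**The case against.** The strongest reply is that this is a contingency the sponsor does not expect, on a secondary endpoint with about 54% planned power, and that the analysis already has a safeguard: SAP 7.3 moves to the Wilcoxon test and to medians when an arm is very asymmetrical. Much of this stands. With no merges there is no effect, and the rank test removes most or all of the damage. The safeguard does not cover means, standard deviations or the t-test if that branch is taken.

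It is also fair that wounds which join have usually lost the skin between them, so the exactly static pair is a limiting case. Like-for-like scoring still counts such a loss, because the skin bridge is in the later area and not in the Visit 2 sum.

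Four stronger readings are tempting and are not supported:

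- *The rule costs the whole fall in Wilcoxon power from 54.6% to 47.0%.* It does not. A like-for-like score already gives 50.6%, because the merged wound pair has healed less than the planning model assumes. The rule accounts for about 3.6 points here, and for none in the static example.
- *The rule works against pAF.* A merge in the SOC arm shifts the result in favour of pAF.
- *Scores far below −100% are to be expected.* They need several neighbours, an enlarging wound, or a larger neighbour that did not itself qualify.
- *The SAP flatly contradicts the protocol.* SAP 7.3 restricts the outcome to the randomised wound but defers to the protocol, which redefines that wound after a merge. The tension is real but partial.

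Finally, summing areas still admits tissue treated with standard of care, and it resets the baseline because of a post-randomisation event. Both points stand, so the like-for-like score should be accompanied by a sensitivity analysis.

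**Conclusion.** The rule as written gives a non-comparable percent reduction whenever it is used, and neither document corrects it. The error in a subject's score depends on the neighbour's size relative to the index wound: −75% instead of 0% for static wounds of 20 and 15 cm², but 0% instead of +20% for a small neighbour.

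At trial level, one pAF merge under the stated assumptions moves the mean difference by about 2 points (12.0 v 14.2), unpooled t-test power by about 14 points (24% v 38%) and Wilcoxon power by about 4 points (47% v 51%). The direction depends on the arm in which the merge occurs. All of this is conditional on at least one merge, for which the documents give no rate. The point is worth settling because it is cheap, but it has low weight and does not threaten the primary safety analysis.

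**What to change.** 1. For a merged wound, use the sum of the component wounds' Visit 2 imaging areas as the denominator at every visit after the merge.
2. Capture Visit 2 images of open wounds near the index wound, whether or not they qualify. At present, data on other qualifying wounds are optional.
3. Add a sensitivity analysis that repeats the comparison with merged wounds scored by the current rule, and report the number of merges by arm.
4. If a neighbour's Visit 2 area is unavailable, do not rely on imputation alone, since that could replace an observed poor outcome with a better one. Also report the result with the observed merged area.
5. State the rule in SAP 7.3, and reconcile the protocol's merge sentence with the SAP's restriction to the randomised wound.

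The cost is a short paragraph in each document, some extra photographs and area tracings at Visit 2, and one more sensitivity analysis. The rule should be fixed before any results by arm are seen.

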### **Sample Size Justification**

A sample size of  $n = 30$  patients per group (total  $n = 60$ ) is expected, though this may differ slightly because of the randomization procedure. Thirty participants in the pAF group with no related serious adverse events will provide a lower-bound of the 95% one-sided exact binomial confidence interval for safety of 90% and provide enough evidence to move on to the next phase of study.

## **9 - DATA MANAGEMENT**

### Clinical Site Data Management

The Data Coordinating Center (DCC) will develop an electronic data capture system for this trial. Currently the DCC uses multiple applications, such as OpenClinica or REDCap, and will elect to use the most appropriate application at the time of implementation of the study.

The DCC will use an electronic discrepancy management system to notify sites of inconsistent or erroneous data entry, which will be corrected by the clinical site. The discrepancy management system maintains an audit trail of all discrepancy resolution.

### Study Monitoring

The investigators recognize the importance of ensuring data of excellent quality. Study monitoring is critical to this process. Monitoring has been a very effective tool for maintaining data quality in previous network studies, and we will utilize this process to ensure excellent quality data in the proposed study. The DCC utilizes risk-based methodology to identify and correct problems that may arise at sites. The risk-based approach to monitoring focuses on oversight activities and preventing or mitigating key risks to data quality, as well as to processes critical to human subject protection and integrity of the trial or study.

Study monitors must be provided with appropriate access to study materials and the medical records for study subjects. If the medical records are in electronic form, the clinical investigator or an authorized individual must provide any assistance necessary to facilitate the study monitor's review of data in the electronic medical record.

### Site Monitoring Plan

A supplemental study-specific risk-based monitoring plan, separate from the protocol will be completed which outlines specific criteria for monitoring. This plan may include the number of planned site visits, criteria for focused visits, additional visits or remote monitoring, a plan for chart review and a follow up plan for non-compliant sites. The monitoring plan also describes the type of monitoring that will take place (e.g., sample of all subjects within a site; key data or all data), the schedule of visits, how they are reported and a time frame to resolve any issues found.

#### Clinical Site Monitoring

Site monitoring visits will be performed by a trained site monitor during the study period to ensure regulatory compliance, patient safety, and to monitor the quality of data collected. Essential document binders, regulatory documents and data collection forms may be reviewed. Interim visits will take place depending on grant budget, site enrollment, and compliance issues identified. The site monitor will provide each site with a written report, and sites will be required to follow up on any deficiencies. It is anticipated that the study monitoring visits for this protocol will consist of a site initiation visit (prior to patient enrollment), interim visits, and a close-out visit. The site initiation may take place as group training made up of site investigators and research assistants.

#### Remote Monitoring

The Data Coordinating Center may supplement on-site monitoring with remote monitoring activities. Remote monitoring involves detailed review of the data entered by the site and consultations with the site investigator and/or research coordinator to review safety and data quality. This may require uploading copies of medical records, patient study files, regulatory documentation, or other source documents for the monitor to review. Alternatively, other methods, such as remotely viewing source documentation, may be utilized. This helps assure protocol compliance and accurate data collection. The Data Coordinating Center may conduct more remote monitoring activities early in the trial to assure protocol compliance and identify any training issues that may exist. Remote monitoring documents will be retained in accordance with federal requirements.

## **10 - PROTECTION OF HUMAN SUBJECTS**

#### Institutional Review Board Approval

The Data Coordinating Center and each clinical center must obtain approval from their respective IRBs prior to participating in the study. The Data Coordinating Center will track IRB approval status at all participating centers and will not permit subject enrollment without documentation of initial IRB approval and maintenance of that approval throughout subsequent years of the project.

